2. Family members (as defined by relatives living in the participants’ household or relatives the participants identify as living in the study community) will be eligible to participate if: i) they participated in at least one of the storytelling sessions; ii) are 18 years of age or older; iii) are able to give informed consent; and iv) are willing to participate in the interview.

c. Exclusion Criteria:

1. Couples will not be eligible to participate in the study if the woman is not pregnant, if she is HIV-positive or if her partner is not HIV-positive, if either person is younger than 18 years, if one member of the couple is unwilling to enroll in PrEP/ART or consent to the infant record search, or if one member of the couple is unable or unwilling to give informed consent for any reason.
2. Family members will not be eligible to participate in the study if they do not participate in at least one storytelling session, if they are younger than 18 years old, if they are unable or unwilling to give informed consent for any reason (e.g. have been drinking or show other signs of mental limitations), or if they are not willing to participate in the interview.

d. Calculations of Sample Size:

Objectives 1 & 2: Our pilot will involve 70 couples (70 HIV-negative pregnant women and their HIV-positive male partners; 35 couples in each arm) from a single clinic. Limited data on PrEP in Mozambique suggest 55% of pregnant women were not retained at 3 months after PrEP initiation. Given our sample size of 70 women and a 5% type I error, we will have 82% power to detect a RR of 0.40 for not being retained. Should there be evidence the intervention effect is similar for men and women with regards to retention, the two groups can be analyzed together to further improve power to detect RRs closer to 0.50. We do not have estimates of Tenofovir levels among PrEP users, but other studies indicate as many as 70% may have no active drug detected.[76]

Given our sample of 70 women and a 5% type I error, we will have 85% power to detect a RR of 0.50 for no detectable drug level.

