Analyses will follow an intent-to-treat protocol. We will estimate the intervention effect on mean outcome scores using separate *linear regression* models for each outcome. If any outcome demonstrates a skewed distribution, we will consider score transformation. Generalized estimating equations (GEE) with an exchangeable working correlation structure will be used to account for clustering within couples. Each model will also include an interaction term between treatment arm and gender to identify gender-specific effects. Given the small sample size and low power of homogeneity tests, if the p-value for the interaction term is ≥ 0.20 , we will also report the

intervention effect for men and women combined (no interaction term). We will not be powered to detect other intervention effect modifiers unless gender is not a modifier, in which case we will explore modification by baseline values of the outcome being analyzed (e.g., is the intervention more effective at improving partner/family support among participants with low partner/family support at baseline), again using an interaction p-value <0.20 as our criteria for evidence of modification of the intervention effect. Finally, given the small sample size of this RCT, it is possible potential confounders remain imbalanced between treatment arms. We will repeat the above analyses (which already include gender), further including age and the baseline value of the outcome being analyzed, to adjust for residual confounding. The small sample, however, precludes from including additional covariates beyond these.

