Secondary analyses will also follow intent-to-treat protocol, again operationalizing the outcomes in the negative (monthly count of missed doses; monthly nonadherence) such that the rate or risk ratios will be <1.0 if the intervention is effective. We will estimate the intervention effect on the count of monthly missed doses using a negative binomial regression model to account for overdispersion due to an excessive amount of zero missed doses (perfect adherence). In addition to clustering of couples, each participant will have up to three observations (one for each month of follow-up). Participants LTFU will only contribute an observation for each completed month of follow-up for which there is a pill count, otherwise they are censored. Similarly, self-reported monthly nonadherence is likely to be heavily skewed with a large proportion of 0% nonadherence. As this is inherently a continuous measure (rather than a count), we will dichotomize as 0% nonadherence vs. $>0\%$ nonadherence and each participant will contribute an observation for each completed month of follow-up. A sensitivity analysis will be performed with dichotomization at $\leq 10\%$ nonadherence vs. $>10\%$ nonadherence. As for the prior analyses, we will utilize GEE models (accounting for clustering of couples and repeated measures on individuals) with an interaction term between intervention arm and gender and will explore modification and adjustment for other covariates as described in Aim 1.

Objective 3: Following completed interviews, audio files will be transcribed by the interviewer, and the PI will code and analyze the interviews using MAXQDA 12® software. Framework Analysis will be used to identify responses to questions about the drivers, core facilitators, and barriers to intervention acceptability and success using grounded theory.[86] Two code maps will be developed to categorize data: (1) to understand the social, structural, and informational drivers, facilitators, barriers to recruiting, providing services for, and supporting discordant couples in

couple-based ANC and post-natal care; and (2) to understand concepts of “best-practice” for scaling up and implementing these services, particularly in regards to family engagement and using stories for educational purposes.

11. Ethical Considerations

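### The monthly adherence models specify no term for month, so if retention differs by arm, any time trend in adherence biases the pooled ratio, in a direction that depends on the trend

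*Combined protocol and SAP*

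**What the plan says.** The point concerns the secondary analyses under Objective 2 in section 10 (Data Analysis): monthly missed doses by negative binomial regression, and monthly self-reported nonadherence as any versus none, with a sensitivity version cut at 10%.

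- **Data structure.** The plan says "each participant will have up to three observations (one for each month of follow-up". For missed doses, "Participants LTFU will only contribute an observation for each completed month of follow-up" and only where a pill count exists. Nonadherence likewise uses completed months.
- **Model terms.** The models are GEE with arm, gender and arm by gender. Effect modification and adjustment are referred back to Aim 1.
- **Covariates in Aim 1.** Age and the baseline value of the outcome are added to gender. The paragraph then ends: "The small sample, however, precludes from including additional covariates beyond these".
- **Retention.** Section 6 makes better retention an aim of the intervention. Section 7.d states "Limited data on PrEP in Mozambique suggest 55% of pregnant women were not retained at 3 months after PrEP initiation" and that "we will have 82% power to detect a RR of 0.40 for not being retained", with "35 couples in each arm".

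Month is named nowhere as a model term.

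**The concern.** GEE handles the correlation among a person's repeated observations. It does not adjust the mean for when each observation was made. Without month in the mean model, each arm's level is an average over whatever months that arm happens to contribute.

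Randomisation does not protect that mix, because loss to follow-up happens after randomisation and may be affected by the intervention. If one arm keeps more people to month 3, its average leans towards later months. If adherence also changes over the three months, part of the arm ratio reflects calendar position and not the intervention. This happens even when dropout is unrelated to adherence.

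What is at stake is the point estimate. Section 12 says the pilot is meant to pick up signals to support a larger trial. Without month, the adherence estimates would partly depend on the retention result.

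**Working it through.** **1. The plan's own figures.** Inputs from section 7.d: 35 women per arm, 5% type I error (two-sided assumed), 55% not retained in control, RR 0.40, so 0.55 × 0.40 = 22% in the intervention arm. Two-proportion test with pooled variance:

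z = (|p1 − p2|√n − 1.96√(2p̄(1 − p̄))) / √(p1q1 + p2q2)

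- Retention: (0.33 × 5.916 − 1.349) / 0.647 = 0.932, power 82.4% (stated 82%).
- No detectable drug, 70% vs 35%: (0.35 × 5.916 − 1.384) / 0.661 = 1.038, power 85.0% (stated 85%).

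Both reproduce. No power is stated for the monthly models.

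**2. Mix of months.** Take three-month retention R of 45% and 78%. Assume a constant monthly loss rate, so the share completing month m is R^(m/3), and apply the same retention to men.

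| | Month 1 | Month 2 | Month 3 | Sum |
|---|---|---|---|---|
| Control, completing | 0.766 | 0.587 | 0.450 | 1.804 |
| Intervention, completing | 0.921 | 0.847 | 0.780 | 2.548 |
| Control, share of observations | 42.5% | 32.6% | 25.0% | |
| Intervention, share of observations | 36.1% | 33.3% | 30.6% | |

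**3. Pooled ratio with no true effect.** Pooled risk = Σ(share completing month m × risk in month m) / Σ(share completing month m). All monthly risks are assumptions.

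| Assumed level, months 1/2/3 | Control | Intervention | Ratio | A true 0.70 reads |
|---|---|---|---|---|
| 20/30/40% | 28.2% | 29.4% | 1.04 | 0.73 |
| 30/45/60% | 42.4% | 44.2% | 1.04 | 0.73 |
| 10/20/40% | 20.7% | 22.5% | 1.09 | 0.76 |
| 30/30/30% | 30.0% | 30.0% | 1.00 | 0.70 |
| 40/30/20% | 31.8% | 30.6% | 0.96 | 0.67 |
| Missed doses 1/2/4 | 2.07 | 2.25 | 1.09 | 0.76 |

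**4. Other attrition shapes.** The alternatives were linear loss, all loss in month 3, and loss only after month 1. Together with constant loss, rising risks give null ratios of 1.03-1.13 (a true 0.70 reads 0.72-0.79). The falling pattern gives 0.95-0.96 (a true 0.70 reads 0.66-0.67). If all losses fall before the end of month 1, the mix is equal in both arms and the ratio is exactly 1.00 for every trend.

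**5. Size against sampling error.** For 20/30/40% with constant loss, person-months are 70 × 1.804 = 126 and 70 × 2.548 = 178. Ignoring clustering, SE(log RR) = √(0.718/(126 × 0.282) + 0.706/(178 × 0.294)) ≈ 0.18. The shift is ln 1.043 = 0.042, about 0.2 standard errors. At the far end (10/20/40%, loss only after month 1, ratio 1.13), the same formula gives √(0.805/(152 × 0.195) + 0.779/(187 × 0.221)) ≈ 0.21. The shift of ln 1.13 ≈ 0.12 is then just under 0.6 standard errors, and less once clustering is counted.

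**6. Does a month term correct it?** Exchangeable Poisson GEE was simulated with 4,000 couples per arm, dropout unrelated to adherence, and risks of 20/30/40% or 30/40/50%. Monte Carlo error is about 0.02-0.03.

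- True RR 1.00: 1.03-1.05 without month, about 1.00 with it.
- True RR 0.70: 0.72-0.75 without, 0.69-0.71 with.
- At trial size (600 simulated trials of 70 couples), standard errors with and without month hardly differ: 0.147 and 0.146 for nonadherence, 0.227 and 0.225 for missed doses.

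**7. What it does not correct.** If poorer adherers leave earlier (assumed correlation 0.5, same rising risks), a true RR of 1.00 reads 1.14-1.24 without month and still 1.10-1.18 with it.

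**The case against.** Much of the opposing case stands.

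- **Direction.** A reader might infer that the better-retained arm is loaded with later, worse months, so that an ineffective intervention would look harmful or a real benefit would be hidden. The documents do not support that. They report no adherence by month and nowhere say it declines. A falling risk reverses the sign, and a flat one removes the bias.
- **Size.** Even with rising risks, a true 0.70 is attenuated to 0.72-0.79, not hidden. In the trial-size simulations the shift is about 0.2-0.4 standard errors (1.03 with SE 0.147; 1.10 with SE 0.227). For missed doses of 1/2/4 with no true effect, false-positive rates were 9.2% without month and 6.8% with it. With Monte Carlo error of about 1 point each, that contrast deserves little weight.
- **Retention gap.** RR 0.40 is the effect the trial can detect in women, not a forecast. No ART retention figure is given for men; if theirs does not differ by arm, their ratio carries no such bias. With a non-retention RR of 0.70 (61.5% retained) and 30/45/60%, the null ratio is only about 1.02.
- **Covariate limit.** The sentence closes a paragraph on chance imbalance in Aim 1 scores, measured at baseline and three months. It may not have been meant to cover month. That makes it silence rather than a deliberate exclusion, but the monthly models borrow that list, and read literally it leaves month out.
- **Standing.** These are secondary analyses in a pilot. The Objective 2 primary endpoints are analysed separately and are not shown to be affected.

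None of this supplies a reason to leave month out. An unknown direction is itself a reason to settle the term before the data are seen.

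**Conclusion.** The concern holds in a conditional form. The secondary monthly models pool up to three months per person, end at loss to follow-up and specify no month term. If retention differs by arm and adherence changes over time, the pooled ratio is biased, towards or away from benefit according to the trend.

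The size rests on assumed monthly risks and attrition shapes, 45% vs 78% retention applied to both sexes, and dropout unrelated to adherence. On those terms the distortion is modest and secondary. It is worth correcting because the remedy costs almost nothing and separates the adherence estimate from the retention effect. Selective loss of poorer adherers could be the larger problem, and it is a separate one.

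**What to change.** In section 10, Objective 2 secondary analyses, add one clause: month of follow-up (1, 2, 3) enters as a categorical fixed effect in the GEE models for missed doses, for any nonadherence and for the 10% sensitivity version, with and without the age and baseline adjustment. State that the Aim 1 limit on covariates does not apply to month. Make the change before outcome data are reviewed, so that it is not a discretionary choice.

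Add a sentence saying that the month term does not address poorer adherers leaving earlier, so the results are to be read with that limit. A sensitivity analysis for such dropout would be a sensible companion.

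The cost is two parameters per model and, in simulation, essentially no loss of precision. No data beyond those already planned are needed.

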37. Patient status (active, default, LTFU, transfer, or death) every month after enrollment;
38. Dates of all PrEP/ART pick-ups
39. Dates of all next scheduled PrEP/ART pick-ups;
40. Dates of all clinic visits
41. Dates of all next scheduled clinic visits;
42. Date cotrimoxazole (CTX) prescribed;
43. Patient reported use of intravenous (IV) drugs;
44. Patient reported use of tobacco;
45. Patient reported use of alcohol;
46. Estimated due date of pregnant female patient;
47. Initiation of any family planning method (Depo, pill, intrauterine device (IUD), implant, condoms, lactational amenorrhea [LAM], tubal ligation, vasectomy [male partner]), and date of initiation;
48. Continuation of any family planning method (Depo, pill, IUD, implant, condoms, LAM, tubal ligation), and date of continuation;
49. Final patient outcome status and date of final status:
 - a. Transfer out of care at that facility, and date of transfer out;
 - b. Death, date of death recorded, cause of death where available;
 - c. LTFU, date of most recent visit (LTFU defined as not returning for >60 days past last scheduled appointment / pick-up date);

- 50. Number of babies with this pregnancy;
- 51. Concentration of PrEP in patient urine;
- 52. Monthly patient self-report of adherence using this scale:

(for each baby, if multiple live births this pregnancy)

- 53. Date of birth of infant(s);
- 54. Infant status at birth (alive, dead);
- 55. Sex of infant(s);
- 56. Weight of infant(s) at birth, and at all other clinic visits, and date of documentation;
- 57. Whether infant(s) received ART prophylaxis after birth, date of start, and type of ARV;
- 58. Data on infant feeding practices where available;
- 59. Date of any PCR testing for infant(s), and test results;
- 60. Date of any HIV rapid testing for infant(s), and test results;
- 61. Data on discharge from CCR services (transfers, referrals, abandoned, died), and date;
- 62. Health status of child(ren) at 18 months (alive, dead);
- 63. HIV health status of child(ren) at 18 months (HIV-positive, HIV-negative)

ANC-specific indicators (aggregated data, from OpenMRS and DHIS databases)

- 64. Number of pregnant women who arrived for first ANC appointment;
- 65. Number of pregnant women who know their serostatus, known positive;
- 66. Number of pregnant women who know their serostatus, recently tested;
- 67. Number of pregnant women who received HIV test results in ANC, first test (positive, negative, and indeterminate results);

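### Self-reported monthly nonadherence is analysed only through cuts at 0% and 10%; a prespecified analysis of the full percentage should stand beside them

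*Combined protocol and SAP*

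**What the plan says.** The point lies in the combined protocol and SAP, section 10 (Data Management and Analysis), in the Objective 2 paragraph on secondary analyses. Two adherence measures are handled there, both described as having many zeros.

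- Missed doses: "We will estimate the intervention effect on the count of monthly missed doses using a negative binomial regression model". The full count is used and the effect is a rate ratio.
- Self-reported nonadherence: "As this is inherently a continuous measure (rather than a count), we will dichotomize as 0% nonadherence" against more than 0%. The sensitivity analysis moves the cut to 10%. No analysis of the percentage itself is planned.

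Both use GEE with couples and repeated months accounted for, an arm-by-gender term, and a ratio below 1 if the intervention works. Appendix 1, item 52, lists the source: "Monthly patient self-report of adherence using this scale". The scale itself is not visible in the text available to me, so its resolution is unknown. No mean, spread, share of zeros or power is given for this measure.

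**The concern.** That a measure is continuous is not a reason to cut it, and many zeros do not force a cut either. The log-link model with robust standard error that the plan uses elsewhere in Objective 2 needs a correct model for the mean, not an integer or binary outcome, so it can be fitted to a percentage with many zeros. For skewed Aim 1 scores the plan considers transformation, and for the missed-dose count it chooses a model that tolerates the zeros. Only this measure is cut.

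The 0% cut scores a month with one missed dose the same as a month with none taken. If the intervention reduces how much is missed without making many months perfect, this analysis registers little of it. The Limitations section says the pilot is meant to pick up signals of success for a larger trial, so a missed signal has a cost.

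**Working it through.** **1. The plan's own power figures.** Section 7d gives "35 couples in each arm) from a single clinic". With pooled variance and two-sided 5%:

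- "we will have 82% power to detect a RR of 0.40 for not being retained", with control risk from "55% of pregnant women were not retained at 3 months after PrEP initiation": 0.55 against 0.22. Null SE = √(2×0.385×0.615/35) = 0.116; alternative SE = √((0.2475+0.1716)/35) = 0.109. Power = Φ((0.33 − 1.96×0.116)/0.109) = 82.4%.
- "we will have 85% power to detect a RR of 0.50 for no detectable drug level", with control risk from "other studies indicate as many as 70% may have no active drug detected": 0.70 against 0.35. The same formula gives 85.0%.

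Both reproduce. Neither concerns self-report.

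**2. Why a cut at zero loses information under a proportional effect.** Assume that missed doses per month are negative binomial with mean μ and dispersion α, with control μ = 3 (10% of 30) and treated μ = 1.5. The share of zero months is (1+αμ)^(−1/α). Take one month and 35 people per arm:

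- z uncut = ln 2 / √((1/3 + 1/1.5 + 2α)/35)
- z cut = (p0 − p1) / √((p0(1−p0) + p1(1−p1))/35), where p is the share with any missed dose
- power = Φ(z − 1.96)

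| α | Zeros, control / treated | p0 / p1 | Risk ratio on the cut | z cut / uncut | Power cut / uncut |
|---|---|---|---|---|---|
| 1.5 | 32% / 46% | 0.679 / 0.544 | 0.80 | 1.17 / 2.05 | 21% / 54% |
| 2.5 | 42% / 54% | 0.575 / 0.464 | 0.81 | 0.94 / 1.67 | 15% / 39% |
| 4 | 53% / 61% | 0.473 / 0.385 | 0.81 | 0.75 / 1.37 | 11% / 28% |

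Halving the amount missed appears on the cut scale as a risk ratio of only about 0.8. The ratio of squared z values shows that the cut keeps about 30% of the information.

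**3. Simulation on the trial's layout.** 35 couples per arm, three months, same mean, ratio and range of zeros (32-53%), proportional effect:

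| Analysis | Power |
|---|---|
| 0% cut | 19-43% |
| 10% cut | 35-71% |
| Uncut percentage | 52-85% |

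The high ends go with 32% zeros and the low ends with 53%. Fitting the proposed model itself (Poisson-family GEE on the percentage, couple clusters, bias-reduced standard error, 400 runs per setting) gave 46% for the 0% cut against 84% uncut, 27% against 65%, and 22% against 57%, at 32%, 43% and 52% zeros. There were no fitting failures. Rejection under no effect was 6-8% uncut and 3-7% for the cut, so a little of the gain is test size.

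**4. How far the gain survives other assumptions.**

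- Heavy attrition plus error in the reported amounts: the gap between the 0% cut and the uncut percentage falls to about 15-19 points. In one set of runs with 55% attrition, strong reporting error and adjustment for test size, it fell to about 2-10 points.
- A shift along an ordered scale, analysed by ranks: the gain is 10-13 points at 20% zeros, 5-6 at 40%, 3 at 50% and 0-2 at 60-80%.
- The intervention mainly converts nonadherent months into perfect ones: the ordering reverses, with 95-100% for the 0% cut against 52-74% uncut.
- Zeros unchanged and only nonzero amounts halved (35 women per arm): the 0% cut is at chance, about 4-5%, against 46-94% uncut.

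**The case against.** The strongest case for the plan has four parts.

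- **Amount is already analysed.** The missed-dose count is modelled uncut for both partners, and the urine test (women), virologic suppression (men) and retention remain. This stands, and it limits the point to one secondary endpoint. One reservation is that the missed-dose model relies on pill counts, and Appendix 1 lists no pill-count item. That does not show pill counts will not be taken.
- **The 10% cut catches moves from poor to good adherence.** This stands in part. In the figures above it recovers more than half of the gap at 32% zeros ((71−43)/(85−43) = 67%) and about half at 53% ((35−19)/(52−19) = 48%). It should not be dropped.
- **Reported amounts are unreliable.** The background says people overestimate adherence and find it hard to quantify, and that PrEP needs very high adherence. This is a fair reason to keep thresholds, and reporting error does shrink the gain. It is not the reason the plan gives.
- **The mechanism is unknown.** This stands. A rate ratio for pill counts summarises means of another variable; it does not commit the plan to a proportional effect on self-report.

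A reader might infer that the cut discards most of the power, or that improvement short of perfect adherence would show no effect. The documents support neither. They state no distribution and no mechanism; in the simulation on the trial's layout the 0% cut keeps about half the power at 32% zeros (43 of 85) and over a third at 53% (19 of 52); and the 10% cut would see part of such an improvement. Nor does the trial as a whole lose its view of adherence.

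**Conclusion.** The point holds as a gap in a secondary analysis. A percentage the plan itself calls continuous is analysed only through two cuts, for a reason that does not require them. Under a proportional effect the 0% cut gives up about 33 to 42 points of power (52−19 and 85−43) and the 10% cut about 14 to 17 (85−71 and 52−35). This rests on an assumed control mean of 10%, a ratio of 0.5, 32-53% zeros and well-measured amounts. With attrition and reporting error, the loss from the 0% cut is roughly 15-19 points or less. Under conversion to perfect months the 0% cut is the better test, so the case is for adding an analysis, not for replacing the planned one.

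**What to change.** Add to the Objective 2 secondary analyses a prespecified analysis of percent nonadherence on its full scale: the same couple-clustered GEE, log link, small-sample-corrected robust standard error and the same arm-by-gender handling, reporting the ratio of mean monthly nonadherence. Report it alongside the 0% cut and keep the 10% cut as the sensitivity analysis. If the item 52 scale is categorical, state the percentage assigned to each category.

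The cost is a sentence or two of analysis text and no new data. The downside is one more secondary estimate to report and interpret, and it is weaker than the 0% cut if the effect is only on perfect adherence. Reporting both covers both mechanisms.
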